- Amendment 10 forming integrated protocol Version 7.0, dated 21 NOV 2019
- Amendment 11 forming integrated protocol Version 8.0, dated 17 FEB 2020
- Amendment 12 dated 06 OCT 2020 (local amendment, valid for Turkey only)

2. Study Objectives

The primary objective of this study is to evaluate the safety of vilaprisan in subjects with uterine fibroids in comparison to nonhormonal medical treatment in accordance with local standard of care.

The secondary objective of this study is to evaluate the efficacy of vilaprisan in subjects with uterine fibroids in comparison to nonhormonal medical treatment in accordance with local standard of care. With the implementation of Protocol Amendment 10 (version 7.0), additional focus will be put on safety evaluations of the endometrium, adrenal glands and skin.

Other objectives of this study are to evaluate the variability in exposure in relation to the efficacy and safety for vilaprisan and to collect patient-reported outcome (PRO) and clinician-reported outcome (ClinRO) data.

3. Study Design

This is an open-label, parallel-group, randomized, multi-center study.

The study was planned to be conducted in Europe, North America, South America, South Africa, and Asia Pacific.

Originally it was planned to randomize 1050 subjects into the study. However, recruitment into the study and treatment in the study were stopped earlier than planned.

An overview of the originally planned study design (before the modifications in study design introduced with Amendment 9, version 6.0 and subsequent amendments) is shown in [Figure 3-1](#).

Eligible subjects were randomized to one of three vilaprisan treatment groups (Groups A1, A2, or A3) or to the standard of care group (Group B).

The planned treatment duration was about one year (Subgroup 1) or two years (Subgroup 2), respectively. The assignment to the 2 subgroups was done in a sequential manner.

After the end of treatment (EoT), subjects were planned to be followed up for 24 weeks (Subgroup 1) or for 12 weeks (Subgroup 2).

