4.5 Data Rules

Reference Start/End dates

For vilaprisan (VPR), the reference start and end dates refer to the first and last study drug intake and will be identified based on the eCRF entry (EXCATN=1). For subjects with study drug exposure unknown, the randomization date will be used as the reference start date, and the end date of last scheduled/ unscheduled visit according SV (Subject Visits dataset) will be used as the reference end date.

Missing or partially missing eCRF end dates will be replaced by the date of the last study drug intake according to the diary. In case there is no study drug intake recorded in the diary, the date of the last available visit/contact will be used, which is the maximum of the end date of last scheduled/ unscheduled visit according SV (Subject Visits dataset), and the “last visit” as collected on the eCRF page for Disposition dataset. For subjects randomized to VPR who did not take any treatment (FAS not SAF), the last available visit date will be used as the reference start date and the reference end date.

For treatment group B the reference start date is defined by the randomization date. The reference end date is defined by the start date of the End of Treatment (EoT) visit (unscheduled EoT visits not considered). Missing EoT visit dates will be replaced by the end date of the last available visit before the safety closeout visit (refer to Table 4-1). If a subject in treatment group B has no safety

closeout visit, missing EoT visit dates will be replaced by the date of last scheduled/ unscheduled visit according SV (Subject Visits dataset).

For both VPR and treatment group B, the reference end date after the missing replacement with the rules defined above should be no earlier than the reference start date. Otherwise, the reference end date will finally be replaced by the reference start date.

For any analysis, if date of first study drug exposure/ date of last study drug exposure is used, the reference start/end date for treatment group B defined as above will be used for the analysis in treatment group B, if applicable.

Table 4-1 Replacement rules for missing reference start/end dates and TP start/end dates

	Choice	VPR regimens	Treatment group B
Reference start date	1 st	eCRF	Randomization date
	2 nd	a. If study drug exposure unknown, use randomization date b. If no study drug exposure (FAS not SAF) use SV last visit end date	
Reference end date / Last TP end date	1 st	eCRF	EoT visit start date

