Exit examination	BL, last value within interval																		Exit examination (Start: EoT -7 days); last value within this interval								

Abbreviations: BL: Baseline, TP: Treatment Period, BR: Break (not applicable for Treatment group B), FUP: Follow-up, d: days, m: months.

Treatment periods and breaks will be identified as described above. Baseline/Pre-treatment phase starts with the date of informed consent and ends on the day before the start of the Treatment phase.

The Treatment phase starts and ends with the reference start and end date. The FUP phase starts on the day after the end of the treatment phase and ends on the maximum of the last date at which a visit took place (visit end date), and the “last visit” as collected on the eCRF page. For patients who did not complete the planned schedule of TPs, a break period will be defined after the end of the last TP, as described in the previous subsection ‘Break period’. This break period will be followed by the FUP.

Baseline, Treatment phase, FUP phase, TPs and breaks are subdivided into subsequent periods of different lengths (28, 84, or 168 days). Exit examination time intervals include the baseline measurement, i.e. the last non-missing value before reference start date, and the exit examination which is defined as the last non-missing value at or after the reference end date – 7 days, which is per definition the safety closeout visit for subjects who perform this visit.

For treatment group B, consecutive TPs (84-day time intervals) in the treatment phase will be used for intervals B and intervals C. Each TP will be subdivided into subsequent consecutive 28-day periods for intervals D. For intervals for assessing AEs in the treatment phase, consecutive TPs will be ended at day 60 after the reference end date. For the assessment in the follow-up phase, same rules will be used as VPR treatment groups.

Details on time intervals for AE presentation are given in Section 6.5.3.5.

Details on time intervals for BMD presentation are given in Section 6.5.1.

Break period

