All information available at the time of analysis will be included. For example, for a subject allocated to treatment group A1 (3/1 regimen) in subgroup 1 who completed the full planned treatment, the number of bleeding days will be counted from the 1st day of TP1 until the date when a new TP would theoretically start following the end of TP4 and the required bleeding episode that follows TP4, without gaps. If a subject withdrew while receiving treatment in TP3, the number of bleeding days will be considered from the 1st day of TP1 until the date when a new TP would theoretically start following the end of TP3 and the required bleeding episode that follows TP3, irrespective of the length of the incomplete TP3.

For subjects who did not start the next planned TP, due to the study being temporarily paused or any other reasons, as described in the section 'Break period', a theoretical end of break period will be derived in these cases. The number of bleeding days will be counted until the derived end of break period.

The period for evaluation of "number of bleeding days" for the treatment group B starts on the reference start date and ends on the reference end date. A theoretical end of break period following the reference end date will not be generated.

The analysis of the number of bleeding days from these pre-determined evaluation periods will be normalized to 28 days and 365 days.

Onset of amenorrhea for analysing time-to-event data

Onset of amenorrhea is defined by the first day for which the menstrual blood loss (assessed by MP) for all subsequent 28-day periods up to the end of the treatment period is <2 mL. Amenorrhea status will be assessed for each of the subsequent, overlapping 28-day periods within a treatment period. The censoring mechanism is assumed to be non-informative and the subjects will be handled as right-censored, if applicable. If a subject completed the 84 days of a treatment period and did not experience an onset of amenorrhea, the subject will be censored on Day 57 of the treatment period.

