6.5.1 Primary safety variable

The primary safety variable is the percentage change in BMD of lumbar spine (using the central reading results) from baseline to about one year after SoT. One year is defined as ‘Month 12 on treatment’ in Table 6-1, i.e. Day 300 after reference start date to Day 420 after reference start date, but no later than the reference end date + 60 days.

The primary safety variable will be analyzed using descriptive statistical methods and two-sided 95% confidence interval (CI) for the mean difference for the percentage change in BMD of lumbar spine from baseline to about one year after SoT will be calculated for each vilaprisan treatment group as compared to treatment group B. Additionally, two-sided 95% CI for each treatment group will be calculated. The primary variable is assumed to be at least approximately normally distributed.

For the percentage change in BMD of lumbar spine from baseline to other time points defined in Table 6-1, the descriptive statistics will also be provided by treatment group.

The percentage change in BMD of lumbar spine from EoT BMD will also be evaluated using summary statistics by treatment group and time interval or month for post treatment period defined in Table 6-1.

The time intervals and month named in Table 6-1 will be presented in tables and figures unless otherwise specified. Month equals 30 days.

Table 6-1: Definition of month and time intervals for BMD summary

	Month	Time interval
Baseline	Baseline	Baseline if no Visit 2-repeat scan exists, Visit 2 scan will be used as baseline. Otherwise, Visit 2 -repeat scan will be used. The BMD baseline visit will be marked in the dataset transferred from ICON’s Medical Imaging group. (refer to section 4.5)
On treatment period : From reference start date to reference end date + 60 days	Month 1	N/A
	Month 2	If a BMD value performed after the reference start date has been marked as baseline value, it will be analyzed as baseline value and will be excluded from the analysis for on treatment period.
	Month 3	
	Month 4	
	Month 5	Month 6 on treatment Day 120 after reference start date to Day 240 after the reference start date, but no later than the reference end date + 60 days
	Month 6	
	Month 7	
	Month 8	
	Month 9	N/A
	Month 10	Month 12 on treatment Day 300 after reference start date to Day 420 after reference start date, but no later than the reference end date + 60 days
	Month 11	
	Month 12	
	Month 13	
	Month 14	

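### Group B's reference end date skips a recorded unscheduled EoT visit and can fall on a follow-up visit, so follow-up time may be analysed as treatment

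*SAP*

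**What the plan says.** Section 4.5 (Reference Start/End dates) gives group B three choices for the reference end date, and Table 4-1 repeats the order.

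- First choice: "The reference end date is defined by the start date of the End of Treatment (EoT) visit (unscheduled EoT visits not considered").
- Second choice: "Missing EoT visit dates will be replaced by the end date of the last available visit before the safety closeout visit".
- Third choice, for a woman with no safety "closeout visit, missing EoT visit dates will be replaced by the date of last scheduled/ unscheduled visit according SV (Subject Visits dataset").

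The only visit type excluded by name is the safety closeout visit, and only under the second choice.

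Group B has a follow-up phase of its own. Section 3 states that after EoT "subjects were planned to be followed up for 24 weeks (Subgroup 1) or for 12 weeks (Subgroup 2"). Section 4.5 (Time intervals) applies the vilaprisan follow-up rules to group B, and sections 6.2.3.1 and 6.2.3.5.1 analyse group B data after the end of treatment separately.

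Several analyses depend on the reference end date:

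- Phase boundary (section 4.5): "The Treatment phase starts and ends with the reference start and end date".
- The secondary efficacy variable (section 4.5): the period for number of bleeding days "for the treatment group B starts on the reference start date and ends on the reference end date".
- Primary BMD window (section 6.5.1): "Day 300 after reference start date to Day 420 after reference start date, but no later than the reference end date + 60 days".
- EoT BMD (Table 6-1): within 60 days either side of the reference end date.
- TEAEs (section 6.5.3.5): up to 60 days after the reference end date.

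**The concern.** Take a group B woman whose EoT visit was recorded only as unscheduled, or not recorded at all, and who then attended follow-up visits. Her EoT date is treated as missing even if an unscheduled one is on file. The replacement is then her last visit before closeout, which is a follow-up visit. Time that the plan itself defines as post-treatment is analysed as treatment, and her follow-up phase before closeout shrinks to nothing. With no closeout visit, the last visit of all becomes her end of treatment and the follow-up phase largely disappears.

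The order is also inconsistent. An unscheduled EoT visit is refused as evidence of end of treatment, yet any unscheduled visit is accepted as the last resort.

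Group B is the comparator for the primary BMD confidence intervals, the bleeding-days variable and the adverse-event tables. A misplaced boundary in this arm therefore affects which control data enter each comparison.

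**Working it through.** The SAP gives no figure to reproduce; the check is date arithmetic on its rules.

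**Inputs.** Planned follow-up (section 3): 24 weeks = 24 × 7 = 168 days in Subgroup 1, and 12 weeks = 12 × 7 = 84 days in Subgroup 2. Month 12 window (section 6.5.1): Day 300 to the earlier of Day 420 and end + 60. EoT BMD window (Table 6-1): end ± 60. TEAE cut-off (section 6.5.3.5): end + 60.

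**Assumption.** The last follow-up visit falls the full planned time s after the true end T. The values of T below are illustrative. The plan sets no limit on s, so late visits would lengthen it and an early closeout would shorten it.

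**Formulas.** Replacement end date = T + s. TEAE cut-off moves from T + 60 to T + s + 60. The EoT BMD window moves from T ± 60 to (T + s) ± 60. The Month 12 upper limit moves from min(420, T + 60) to min(420, T + s + 60).

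| T | s | Replacement end | TEAE cut-off | EoT BMD window | Month 12 window |
|---|---|---|---|---|---|
| 120 | 84 | 204 | 180 → 264 | 60–180 → 144–264 | none → none |
| 120 | 168 | 288 | 180 → 348 | 60–180 → 228–348 | none → 300–348 |
| 200 | 84 | 284 | 260 → 344 | 140–260 → 224–344 | none → 300–344 |
| 200 | 168 | 368 | 260 → 428 | 140–260 → 308–428 | none → 300–420 |
| 300 | 84 | 384 | 360 → 444 | 240–360 → 324–444 | 300–360 → 300–420 |
| 300 | 168 | 468 | 360 → 528 | 240–360 → 408–528 | 300–360 → 300–420 |
| 365 | 84 | 449 | 425 → 509 | 305–425 → 389–509 | unchanged, 300–420 |
| 365 | 168 | 533 | 425 → 593 | 305–425 → 473–593 | unchanged, 300–420 |

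**Intervals.** The shift adds 84 / 84 = 1 or 168 / 84 = 2 treatment periods, that is 3 or 6 periods of 28 days. The TEAE window closes 144 or 228 days after the true end instead of 60.

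**Primary BMD window.** With the true date, a Month 12 scan is possible only if T + 60 ≥ 300, so T ≥ 240. With the replacement, T ≥ 240 − 84 = 156 or T ≥ 240 − 168 = 72 is enough. The window is complete under either date once T + 60 ≥ 420, so nothing changes for T ≥ 360. For T = 120, a scan on Day 300 (180 days after the true end) enters under the 168-day shift (cap Day 348) but not under the 84-day shift (cap Day 264).

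**Bleeding days.** Suppose 6 bleeding days per 28 up to T = 120, which is 6 / 28 × 120 = 25.7 days. If bleeding continues at the same rate in follow-up, the normalised result stays at 6.0. If it stops entirely, the result is 25.7 / 204 × 28 = 3.5 or 25.7 / 288 × 28 = 2.5. Both rates are assumptions; the SAP gives neither.

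**BMD recovery.** EoFUP BMD must be no earlier than 60 days after the reference end date (Table 6-1). If that date is the last visit of all, such a scan is practically impossible and the woman has no recovery status in Table 6-2.

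**The case against.** The strongest defence is that the rule was written for a different case. Section 3 describes group B women still in the study at Amendment 10 who go on to the safety closeout visit. If such a woman went there directly from treatment, her last visit before closeout is a treatment visit and the rule returns a sensible date. It is also harmless when the unscheduled EoT visit is itself the last visit before closeout. This stands.

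Failure needs both a missing scheduled EoT visit and a later follow-up visit. Whether that occurred depends on a visit schedule not shown here, and nothing in the SAP shows that the number is above zero. An unscheduled EoT visit may also be an extra one alongside a scheduled visit, in which case ignoring it is right. This limits the weight of the point but does not supply the missing restriction.

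For women on watch and wait no study drug stops, so the boundary is partly a visit label. That is fair, but the plan still analyses the two phases separately.

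Last-visit replacement is used for vilaprisan too. There, however, it comes only after the last intake in the diary has been tried; group B has no such intermediate step.

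A reader might infer that the affected women left standard of care early to change therapy, so that the control arm is contaminated in a known direction. The SAP says nothing about why such women stopped or what they took next. The date and window errors do not depend on that inference, and the falls to 3.5 and 2.5 bleeding days are illustrations only.

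**Conclusion.** The defect is in the text: a recorded unscheduled EoT date is ignored, and neither replacement excludes follow-up visits. Per affected woman, up to the planned 84 or 168 days are moved from follow-up to treatment, assuming she completed her planned follow-up. The bleeding-days period, TEAE window, Intervals A to D and EoT BMD window move with them. The Month 12 cap changes only for true ends before Day 360. Treatment duration is unaffected, because section 6.1.8.1 uses no date replacement.

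A reader might go further and conclude that the primary BMD comparison is materially biased. The documents do not support this: the number of affected women is not given, and nothing in the SAP shows a group B scan falling where the window would wrongly admit it. The point is a minor one, worth correcting because the correction is easy.

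**What to change.** In section 4.5 and Table 4-1, set the group B reference end date as follows:

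1. Start date of the scheduled EoT visit.
2. If there is none, the date of the unscheduled EoT visit.
3. If there is neither, the last visit whose visit label is not follow-up, safety closeout or later.

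Step 3 must work from visit labels. Limiting it to the treatment phase would be circular, because section 4.5 defines that phase by the reference end date. Step 2 acts only when no scheduled EoT visit exists, so it leaves alone any unscheduled visit that merely duplicates a scheduled one. If excluding unscheduled EoT visits was deliberate, the SAP should say why and still apply the restriction in step 3.

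The cost is a wording change, a small change to the derivation and a list of visit labels, which the SAP does not now contain. The dates are recorded visit dates, so no new data are needed.

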With the implementation of protocol amendment 9 (Version 6.0), no further subjects were recruited. Subjects that started to a regimen with 3-months treatment courses should finish the treatment course as planned. Subjects that started to a regimen with treatment courses of 6 months duration should finish the first 3 months, if they are currently in the first 84 days of that treatment course, finish the second 3 months, if they are currently beyond day 84 of the treatment course. Thus, with the implementation of protocol amendment 9 and the originally foreseen study design outlined in [Figure 3-1](#) is not applicable anymore for vilaprisan groups. Subjects in treatment group B can continue the study course following the current valid version of the protocol.

With the implementation of Protocol Amendment 10 (version 7.0), this study design as outlined in [Figure 3-1](#) is no longer valid. No subjects will receive further study drug treatment. All subjects who were randomized and started treatment before the temporary pause were asked to have a comprehensive safety evaluation (with particular focus on endometrial, adrenal and skin safety) performed. This also applies to subjects who have completed or discontinued the study before or during the temporary pause, provided they have taken at least one dose of study medication.

Likewise, subjects randomized to treatment group B who are still in the study will be asked to undergo these procedures.

At the time study treatment was terminated, no subjects in subgroup 2 had reached the second year of treatment. Therefore, the statistical analysis will include patients from both subgroups without any distinction.

Figure 3-1 Design overview

Subgroup 1 (about 1 year of treatment)

A1	SCR up to 90 days	RND	12 wk trt	B	12 wk trt	B	12 wk trt	B	12 wk trt	24 wk FUP
A2	SCR up to 90 days	RND	24 wk trt		B	B	24 wk trt		24 wk FUP	
A3	SCR up to 90 days	RND	12 wk trt	B	B	12 wk trt	B	B	12 wk trt	24 wk FUP
B	SCR up to 90 days	RND	Symptomatic nonhormonal medical treatment as determined by the investigators and/or watch and wait						24 wk FUP	

Subgroup 2 (about 2 years of treatment)

A1	SCR up to 90 days	RND	12 wk trt	B	12 wk trt	B	12 wk trt	B	12 wk trt	B	12 wk trt	B	12 wk trt	B	12 wk trt	B	12 wk trt	12 wk FUP
A2	SCR up to 90 days	RND	24 wk trt		B	B	24 wk trt		B	B	24 wk trt		B	B	24 wk trt		12 wk FUP	
A3	SCR up to 90 days	RND	12 wk trt	B	B	12 wk trt	B	B	12 wk trt	B	B	12 wk trt	B	B	12 wk trt	B	B	12 wk FUP

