	2 nd	Diary	Last visit before the safety closeout visit
	3 rd	Max (SV last visit end date, “last visit” from eCRF)	SV last visit end date
	4 th	If no study drug exposure (FAS not SAF) use SV last visit end date	
		Reference end date will finally be replaced by maximum of reference start date and reference end date.	
TP start date	1 st	eCRF (TP1: reference start date) Exception 6/2 regimen: split protocol planned TPs with 168 days, assign start and end dates of these with CRF collected for planned TPs and derived start and end dates of split TPs.	TP1: reference start date TPs will be defined as consecutive 84-day time intervals starting with the date of randomization.
TP end date (excluding last TP)	1 st	eCRF exception 6/2 as above	
TP end date (last TP)	1 st	Reference end date	

eCRF = electronic case report form; EoT = end of treatment; SV=subject visit; TP = treatment period; VPR = vilaprisan

Treatment period

For subjects in treatment groups A1, A2, and A3, each treatment period (TP) consists of three subsequent 28-day periods. In case of premature discontinuation of study drug the last 28-day period of the respective treatment period might be shorter than 28 days. If a subject took the study drug for more than 84 days of a treatment period, the respective treatment period will be longer than 84 days, in contrast. Subjects treated in 3/1 and 3/2 regimens, have the first break after TP 1. Subjects treated in 6/2 regimens have two planned TPs before the first break.

The definition of TP here described which will be used in the analysis, differs from the definition of TP used in the protocol and Section 3 to describe the 6/2 treatment regimen. The definition used in the analysis allows for a better comparison between treatment regimens and is consistent with the reporting of other studies of the VPR project.

The first TP starts with the reference start date, the last TP ends with the reference end date. Start and end of a TP will be identified based on eCRF entries (EXCATN=1).

In 6/2 regimen, the protocol plans for TPs with 168 days each. The CRF only collects start and end dates of these protocol planned TPs.

For the analysis, the planned protocol TPs are split into 2 Analysis TPs:

- The first Analysis TP is assigned first available odd TP number and ends with day 84 (or the maximum number of available days if less than 84 days are reported).

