- The second Analysis TP is assigned the next higher even TP number, starts with day 85 and ends with the last day reported in the original protocol TP, even if this exceeds a total of 168 days.

For example, protocol TP1 = analysis TP1 + analysis TP2. Protocol TP2 = analysis TP 3 + analysis TP 4 etc.

If the original planned protocol TP is less than 85 days, no such second evenly numbered Analysis TP will be assigned. As a result of this a subject in 6/2 regimen might have Analysis TP 1, TP 3 and TP 4, but no Analysis TP 2.

If the end date of the current treatment period is equal to the start date of the next treatment period based on CRF entries, it is assumed that the current treatment period ended one day earlier. The end date of the current treatment period is therefore moved back by one day.

For all TPs excluding the last TP, in case end of TP date is still missing, it will be replaced by the date of the last study drug intake within the respective TP according to diary (EXCATN=5 and EXMEDN>=1).

Subjects in treatment group B don't have any breaks. In the treatment group B TPs will be defined as consecutive 84-day time intervals starting with the date of randomization.

Replacement rules for missing end date of the last TP are analogue to those described for reference end dates.

TPs will be numbered sequentially.

Time intervals

Due to the complex visit schedule of the studies, a time-interval based approach is chosen to present data over time. Therefore, time intervals are defined which are used for different analysis topics.

The selection of time intervals used for a certain analysis topic will be described within each section.

An overview of the time intervals is given in [Figure 4-1](#).

Figure 4-1: Time interval overview

BL/Post baseline	Post baseline																										
Intervals A	Treatment Phase																		FUP Phase								
Intervals B	TP1 + BR1						TP2 + BR2						TPx						FUP1+2			FUP ...					
Intervals C	TP1			BR1			TP2			BR2			TPx			FUP1			FUP2			FUP ...					
Intervals D	BL	BL	BL	TP1	TP1	TP1	BR1	BR1	BR1	TP2	TP2	TP2	BR2	BR2	BR2	TPx	TPx	TPx	FUP	FUP	FUP	FUP	FUP	FUP	FUP	FUP	FUP
	1-28	29-56	57-x	1-28	29-56	57-84	1-28	29-56	...	1-28	29-56	57-84	1-28	29-56	...	1-28	29-56	57-84	1-28	29-56	57-84
AE Intervals	Pre-treatment			"on" (TP1 + 8d)			"off"			"on" (TP2 + 8d)			"off"			"on": TPx + 8d			"off"			Post-treatment (Start: day 61 after EoT)					

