This definition of bleeding episode, based on the UF-DBD, is the only bleeding definition implemented in the analysis to identify bleeding episodes. The protocol includes a definition of bleeding episode based on the MP, which will be implemented during the screening period to facilitate the assessment of the HMB inclusion criterion (criterion 4, MBL >80 mL) by clinical sites. This latter definition of bleeding period will not be used in the analysis.

Menstrual blood loss for 28 days

Menstrual blood loss for 28 days is defined as the sum of menstrual blood loss [mL] by MP in a 28-day period. Non-overlapping 28-day periods will be created along the different study periods: TPs, break periods (if applicable), and FUP phase. In case of premature discontinuation of study drug the last 28-day period of the respective treatment period might be shorter than 28 days. For details about the volume of MBL assigned to MP, see Appendix 4.

Volume of menstrual blood loss per bleeding episode after the reference end date

Volume of menstrual blood loss for a bleeding episode is the sum of volume of menstrual blood loss [mL] data by MP in the respective episode after the reference end date.

Amenorrhea (defined as < 2 mL during last 28 days of treatment course) assessed by MP method

Amenorrhea is defined as menstrual blood loss less than 2 mL during the last 28 days of the respective treatment period. For missing data replacement please refer to section 4.3.

- i) the sum of the non-missing (i.e. original or imputed) MP values is ≥ 2 mL, or
- ii) there is at least one day with missing MP value and bleeding intensity of “mild” up to “very severe” after having applied the imputation rules, or
- iii) the subject did not complete at least 8 weeks of treatment.

If neither of i), ii) or iii) applies, the subject will be considered as having amenorrhea.

The last days under treatment with 28 days with non-missing (i.e. original or imputed) MP data will be used to calculate whether amenorrhea occurred. Thus, if the last 28 days of treatment include days with missing MP data, the left margin of this interval will be displaced backwards in time and step-wise until the required number of 28 non-missing values are included.

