The left margin may be displaced backwards at maximum up to the end of the first bleeding episode when treatment was started in respective treatment period. For TP with an even number in the 6/2 regiment, the left margin may be displaced backwards at maximum up to the end of the first bleeding episode of the preceding odd-numbered TP from the same protocol defined 168-day TP when treatment was started.

Absence of bleeding (spotting allowed) during the last 28 days of the treatment; based on the UF-DBD

Absence of bleeding is defined as no bleeding (spotting allowed) during the last 28 days of the respective treatment period based on the UF-DBD. For missing data replacement please refer to section 4.3.

The last days under treatment with 28 days with non-missing bleeding eDiary data will be used to calculate whether absence of bleeding occurred. Thus, if the last 28 days of treatment include days with missing bleeding eDiary data, the left margin of this interval will be displaced backwards in time and step-wise until the required number of 28 non-missing values are included.

The left margin may be displaced backwards at maximum up to the end of the first bleeding episode when treatment was started in respective treatment period. For TP with an even number in the 6/2 regimen, the left margin may be displaced backwards at maximum up to the end of the first bleeding episode of the preceding odd-numbered TP from the same protocol defined 168-day TP when treatment was started.

Subjects who discontinue treatment prior to completion of 8 weeks of treatment in the respective TP will be considered as not experiencing absence of bleeding.

Number of bleeding days

Number of bleeding days is defined as number of bleeding days (based on the UF-DBD) from Day 1 of the first treatment period until one day before the theoretical next treatment period would start after the last study treatment period. Definition of the day before theoretical next treatment period end date, i.e., theoretical end date for the break period, refers to the rules defined in break period above.

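### In the 6/2 regimen, a course stopped at about 3 months that overruns day 84 by a few days gets a very short even-numbered Analysis TP, which is scored as failure for absence of bleeding

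*SAP*

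**What the plan says.** SAP Section 4.5 (Treatment period) defines two kinds of Analysis TP.

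- **General rule.** If a subject takes drug for more than 84 days of a TP, "the respective treatment period will be longer than 84 days, in contrast". This governs the 3/1 and 3/2 regimens (A1, A3).
- **6/2 regimen (A2).** The 168-day protocol TP is split. The first part "ends with day 84 (or the maximum number of available days if less than 84 days are reported"). The second part "starts with day 85 and ends with the last day reported in the original protocol TP". The only condition on creating it is this: "If the original planned protocol TP is less than 85 days, no such second evenly numbered Analysis TP will be assigned".

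Section 6.2.3.1 analyses amenorrhea and absence of bleeding by treatment group and TP. The 8-week conditions for these endpoints, both in Section 4.5, are worded differently.

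- **Absence of bleeding:** "Subjects who discontinue treatment prior to completion of 8 weeks of treatment in the respective TP will be considered as not experiencing absence of bleeding".
- **Amenorrhea, item iii:** failure if "the subject did not complete at least 8 weeks of treatment". The TP is not mentioned.

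Section 3 describes Amendment 9. Subjects on 6-month courses were to "finish the first 3 months, if they are currently in the first 84 days of that treatment course"; those already past day 84 were to finish the second 3 months.

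**The concern.** The split exists so that regimens can be compared over TPs of similar length. Its cut has no tolerance, and Amendment 9 placed planned stops at the same point. An A2 subject who did as instructed and took a few tablets beyond day 84 acquires an even-numbered TP that she was never meant to have. That TP is too short to pass the 8-week condition, so an administrative stop is recorded as non-response. She may count as a success in the odd TP and as a failure in the even TP on nearly the same days of continuous treatment. An A1 or A3 subject with the same overrun has one slightly longer TP, judged on its last 28 days. What is at stake is the A2 rate in the even-numbered TPs (TP 2, and TP 4 if a second course was stopped this way) and its comparison with A1 and A3.

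**Working it through.** The SAP gives no figure to reproduce, so the check applies its rules to a course of L days.

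**Inputs, all from Section 4.5:** odd 6/2 Analysis TP ends at day 84; even Analysis TP is created if L ≥ 85; 8 weeks = 56 days; overruns in 3/1 and 3/2 stay in the same TP; group B is cut into consecutive 84-day intervals.

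**Formulas.** 6/2: odd TP = min(L, 84); even TP = L − 84 if L ≥ 85. 3/1 and 3/2: one TP of L days for the same overrun.

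| Course L (days) | 6/2 odd TP | 6/2 even TP | Even TP ≥ 56 days? | Same overrun in 3/1 or 3/2 |
|---|---|---|---|---|
| 84 | 84 | none | – | one TP of 84 |
| 85 | 84 | 1 | no | one TP of 85 |
| 86 | 84 | 2 | no | one TP of 86 |
| 90 | 84 | 6 | no | one TP of 90 |
| 139 | 84 | 55 | no | not relevant |
| 140 | 84 | 56 | yes | not relevant |

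The even TP first passes at L = 84 + 56 = 140. For every L from 85 to 139 it fails absence of bleeding regardless of the diary.

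**Amenorrhea.** If item iii is read per TP, the result is the same for L = 85 to 139. If it is read over the subject's treatment or the 168-day course, 85 > 56 and there is no automatic failure.

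**Evaluation window.** For even 6/2 TPs, the left margin of the 28-day window may move back into the preceding odd TP, but this provision is tied to replacing days with missing data. Even where it applies, the 8-week count for absence of bleeding is not extended with it. If the window for L = 86 is taken as the last 28 days of treatment, 2 days lie in the even TP and 26 in the odd TP.

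**Group B.** 365 days = 4 × 84 + 29, and 29 < 56, so its last interval can also be too short.

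**Illustration only; neither value is in the SAP.** Let s be the share of A2 even-TP records that are such short TPs, and p the success rate in the rest. The reported rate is p(1 − s).

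| p | s = 5% | s = 10% | s = 20% | s = 30% |
|---|---|---|---|---|
| 0.50 | 0.475 | 0.45 | 0.40 | 0.35 |
| 0.70 | 0.665 | 0.63 | 0.56 | 0.49 |
| 0.90 | 0.855 | 0.81 | 0.72 | 0.63 |

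**The case against.** Several parts of the case against stand.

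- **Amenorrhea.** A reader might infer that amenorrhea fails automatically too. The text does not say so: item iii omits the reference to the respective TP that the parallel rule contains. A per-TP reading is natural because the endpoint is defined and analysed by TP, but it remains a reading.
- **Three months.** A reader might infer that 3 months means about 90 days, so that every A2 subject stopped under Amendment 9 gets a short even TP. Section 3 ties the instruction to day 84 and shows the 3-month courses as 12 weeks. A subject who stops exactly on day 84 gets no even TP. Only overruns matter, and their frequency is not given.
- **One group only.** A reader might infer that A2 alone is exposed. Group B's last interval can also be short, so the contrast holds against A1 and A3 only.
- **Importance.** Both endpoints are other efficacy variables, analysed descriptively in a study whose treatment was stopped early. The primary BMD variable uses reference dates, and the secondary efficacy variable, number of bleeding days, is counted across TPs without gaps. Neither depends on this cut.

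None of this removes the explicit result for absence of bleeding.

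**Conclusion.** As written, the rules give a wrong per-TP response for absence of bleeding in A2 subjects who were to stop after the first 3 months under Amendment 9 and overran day 84. For amenorrhea the result depends on an unclear condition, and that lack of clarity itself needs correcting. The direction is known: the A2 even-TP rate is lowered, by the fraction s in relative terms. The size cannot be given, because the SAP reports neither the number of overruns nor a response rate; the rates shown above rest on assumed values. The odd-TP results in A2 are not distorted. The point deserves correction because the trigger is foreseeable from the SAP's own account of Amendment 9, although the endpoints affected are not leading ones.

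**What to change.** In Section 4.5:

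1. For 6/2 courses that were to end after the first 3 months under Amendment 9, assign no even-numbered Analysis TP. Let the odd Analysis TP extend to the last day of intake, as in A1 and A3.
2. Keep the even TP for subjects who were meant to continue past day 84 and discontinued, so that genuine discontinuations stay in the denominator.
3. State the 8-week condition in identical words for amenorrhea and absence of bleeding, saying whether it counts within the Analysis TP or the 168-day course.

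A minimum course length of 140 days (84 + 56) before an even TP is assigned looks simpler but should not be used. It would drop A2 subjects who genuinely discontinued on days 85 to 139 from the even-TP denominator, while A1 and A3 subjects who stop before 8 weeks of their second TP remain failures.

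**Cost.** A few A2 odd TPs will exceed 84 days. Derivations that depend on TP numbering need a matching update: the time intervals in Figure 4-1, the theoretical end of the break in 6/2 (outside the bleeding-days variable it is generated only if an even TP was started), and the on-treatment AE assignment in Section 6.5.3.5. The courses concerned must be identified from the timing of the course relative to Amendment 9, not from bleeding results.
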